7.6 Pharmacokinetic Statistical Methodology

7.6.1 Summary Statistics

Summary statistics of the individual concentration data and derived parameters will be calculated with the built-in Phoenix[®] WinNonlin[®] platform and displayed with the same precision as received from the bioanalytical laboratory; additional details on precision rules are provided in Section7.7.

Descriptive statistics will be calculated for INDV-2000 and M12 plasma concentrations for each nominal time point and for all PK parameters,

Plasma Plasma individual concentrations and PK parameters obtained from the NCA will be summarized using the following summary statistics: N, minimum (min), arithmetic mean (mean), geometric mean (for main plasma PK parameters only), median, maximum (max), standard deviation (SD), CV%, and geometric CV% (for main plasma PK parameters only).

7.7 Pharmacokinetic Presentation

In general, all PK summary tables will be presented for the PK population.

Individual raw PK concentrations will be displayed with 3 significant digits, unless otherwise recommended.

Precision for individual PK parameters will be displayed as follows:

Protocol No. INDV-2000-101

Version Final 1.0 | 2021/03/30

Page 26 of 46

- C_{max}, AUCs (including dose normalized parameters) and AUC-derived parameters will be displayed with the same precision as the raw PK concentration data
- Parameters associated with time (e.g. t_{max} and $t_{1/2}$) will be displayed with 2 decimal places
- Percentages will be displayed with 2 decimal places

Terminal phase characterization:

- Number of points with 0 decimal place
- R^2 and λ_z with 4 decimal places

Summary statistics for concentration and PK parameters will be displayed with the same precision as the individual values, with the exception of number of observations (N) and coefficient of variation (CV%) which will be presented with 0 and 1 decimal place, respectively.

Concentration profiles will be presented on both linear and semi-log scales. Actual elapsed times of PK plasma sample collection relative to dose administration will be included in the listings.

8 SAFETY ANALYSIS

8.1 Adverse Events

AE monitoring and reporting for each subject will begin after the ICF is signed and will continue throughout the study, including the EOS visit, early termination, and follow-up. Data collected will include reported term, timing, seriousness, severity, toxicity, relationship to IMP, action taken, and outcome. SOCs and PTs for reported terms will be classified using the MedDRA version 23.0 terminology as defined in the study DMP.

8.2 Concomitant Medications

Concomitant medications are defined as medications taken at or after the time of first IMP dose. Data collected will include medication name, timing, dose, route, frequency, formulation, indication, related AEs and related medical history. Drug classes and standardized names for reported medication names will be coded using WHO-Drug Global September 2020 as defined in the study DMP.

8.3 IMP Exposure

IMP administration will be performed on Day 1 in Part I, Part II Period 1, and Part II Period 2. Data collected will include dose, formulation, date/time, route, and whether the subject consumed remainder of 240 mL water, taste masking administered, double rinse was conducted, capsule consumption was verified, and IMP was administered per protocol. For Part II, whether the subject was fasting will also be collected.

8.4 Clinical Laboratory Evaluations

Clinical laboratory data collected will include collection date/time, lab test, result, reference range, out-of-range flag, clinical significance, result and comment.

In the database of laboratory evaluations, results for hematology, chemistry and some urinalysis tests (e.g., specific gravity, pH) will be numeric and results for the remaining urinalysis tests, urine drug screen, serology, and pregnancy tests will be reported as text.

The out-of-range flag will be reported as abnormal, high, low, or normal. Abnormal test results will be further categorized as clinically significant, not clinically significant, repeated, or to be controlled.

Hematology	Serum Chemistry:
Hematocrit	Albumin
Hemoglobin	Alkaline phosphatase
Mean corpuscular hemoglobin	Alanine aminotransferase (ALT)
Mean corpuscular hemoglobin concentration	Amylase
Mean corpuscular volume	Aspartate aminotransferase (AST)
Platelet count	Blood urea nitrogen
Red blood cell count	Calcium
White blood cell count with differential (absolute	

The following clinical laboratory tests will be performed according to the schedule in APPENDIX A:

count)

	Carlana di seri la
count)	Carbon dioxide
	Chloride
Urinalysis:	Creatinine
Appearance	Creatine kinase
Bilirubin	Gamma-glutamyl transferase
Color	Glucose (non-fasting)
Glucose	Lactate dehydrogenase
Ketones	Lipase
Leucocyte esterase	Magnesium
Microscopic examination of sediment ^a	Phosphorus
Nitrite	Potassium
Occult blood	Sodium
pH	Total bilirubin
Protein	Direct bilirubin
Specific gravity	Total cholesterol
Urobilinogen	Total protein
	Triglycerides
Hormone Panel:	
Follicle Stimulating Hormone	Urine Drug Screen (UDS):
	Opioids
Pregnancy:	Cocaine
Serum hCG	Amphetamines
	Cannabinoids
Screening Only:	Barbiturates
Hemoglobin A1c	Benzodiazepines
Hepatitis B surface Antigen	Methamphetamine
Hepatitis C Antibody	Phencyclidine
HIV-1 and -2 antibodies	Ethanol
Prothombin Time (PT) with INR	
PTT	

Anti-HIV = human immunodeficiency virus antibodies; hCG = human chorionic gonadotropin; INR = international normalized ratio; PT = prothrombin time; and PTT = partial thromboplastin time.

а Microscopic examination of sediment will be performed only if the results of the urinalysis evaluation are positive (microscopic examination may include but is not limited to White Blood Cell count, Red Blood Cell count, casts and crystals).

Protocol No. INDV-2000-101

Version Final 1.0 | 2021/03/30

8.5 Vital Signs

Vital signs will include SBP, DBP, respiratory rate, heart rate and temperature. Vital signs will be measured according to the schedule in APPENDIX A. Triplicate SBP and DBP measurements will be done at baseline.

8.6 Physical Examination Findings

Physical examination will include date, time and body system examined. Physical examination will be performed according to the schedule in APPENDIX A. At screening, previously unrecognized findings that are clinically significant will be included as adverse events; other clinically significant findings at screening will be included as medical history. After dosing, any new or worsening findings will be included as adverse events.

8.7 Electrocardiogram

12-lead ECG includes the parameter ECG mean ventricular rate, PR interval, QRS duration, QT interval, QTcF interval and interpretation. 12-lead ECGs will be performed according to the schedule in APPENDIX A. Triplicate measurements will be done at baseline. If a potentially clinically significant (CS) abnormality is noted during other time points, a triplicate ECG will be taken at that time point.

ECG holter monitoring will be recorded on Day 1 from at least 2 hours pre-dose until at least 24 hours post-dose for Part I and Part II. The continuous 12-lead ECG data will be stored on secure digital memory cards for potential transfer to a central ECG laboratory as indicated for QT analyses evaluating the risk of prolonged cardiac repolarization. Whether ECG holter monitoring was performed, start date/time, and end date/time will be recorded in the eCRF.

9 DATA HANDLING AND PRESENTATION

All safety and statistical outputs will be generated using SAS software, version 9.4. Pharmacokinetic outputs will be generated using WinNonlin version 8.0 or higher.

The analyses described in this plan are considered *a priori*, in that they have been defined prior to database lock and/or prior to breaking the blind. Any analyses performed subsequent to database lock and/or breaking the blind that are not described within the present plan will be considered post hoc and exploratory. Post hoc analyses will be labeled as such in the corresponding statistical output and identified in the clinical study report (CSR).

9.1 Study Population and Safety Analysis Presentation

Tables of summary statistics will be presented for the Safety population, separately for Part I and Part II. For Part I, summaries will be presented by dosing cohort for active treatment and for all placebo subjects combined; for Part II, summaries will be presented by period. Summary statistics will be number of observations, mean, standard deviation (SD), median, minimum, and maximum for continuous variables and counts and percentages for categorical variables. For natural log (ln)-transformed endpoints, geometric mean, geometric standard deviation (SD), and coefficient of variation (CV%) will also be presented.

In general, the data listings will include all enrolled subjects and will be presented separately for Part I and Part II. Listings will be sorted by cohort (Part I) or period (Part II) and then by subject.

The following general comments also apply to all statistical analyses and data presentations:

- Study day is defined as (event date-date of first dose) + 1 for event dates on or after the date of first dose, and as (event date-date of first dose) for event dates before the first dose. For Part II, study day will be defined within period.
- Duration will be defined as (end date start date) +1.
- If the reported value of a clinical laboratory parameter cannot be used in a statistical summary table (e.g., a character string is reported for a parameter of the numerical type), a coded value must be appropriately determined and used in the statistical analyses. In general, a value or lower and upper limit of normal range such as '<10' or '≤5' will be treated as '10' or '5' respectively, and a value such as '>100' will be treated as '100'. However, the actual values as reported in the database will be presented in data listings.
- If there are multiple assessments for a given nominal visit or time point, the assessment closest in time to the nominal visit or time point will be used in summary tables; if assessments are equidistant from the nominal time point, the mean of the assessments will be calculated and used in summary tables. Assessments classified as "unscheduled" will not be included in summary tables.

In general, summary statistics for raw variables (i.e., variables measured at the study site or central laboratory) will be displayed as follows:

- Minima and maxima will be displayed to the same number of decimal places as the raw data.
- Means, medians, and quartiles will be displayed to 1additional decimal place.

- Standard deviations will be displayed to 2 additional decimal plac
- Percentages will be displayed to 1 decimal place. Percentages between 0 and 0.1 (exclusive) will be displayed as '<0.1'.
- P-values will be displayed to 3 decimal places. P-values that are less than 0.001 will be displayed as '<0.001'.

The numbers of decimal places for summary statistics of derived variables (i.e., variables that are not measured by the study site but are calculated for analysis based on other measured variables) will be determined on a case by case basis. In general:

- Minima and maxima will be displayed to the commonly used unit of precision for the parameter.
- Means, medians, quartiles, and confidence limits will be displayed to 1 additional decimal place.
- Standard deviations will be displayed to 2 additional decimal places.

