### 8.6 12-Lead Electrocardiograms

A 12-lead ECG will be recorded after the subject has been in the semi-recumbent position for a minimum of 5 minutes as presented in the Schedule of Events tables (Section 22.1. Appendix 1 and Section 22.2, Appendix 2).

A triplicate ECG will be recorded for the determination of the baseline result at pre-dose. The baseline value will be the mean of the 3 recordings. If a potentially clinically significant abnormality is noted during other ECG assessments, a triplicate ECG will be taken at that timepoint. All triplicate ECG recordings should occur at least 1 minute apart. If a subject shows an abnormal assessment at any stage, repeat measurements may be made and the abnormality followed to resolution, if required. Additional measurements may be taken as deemed necessary by the Investigator.

Any clinically significant abnormalities, including changes from baseline, will be reported as AEs.

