#### 22 APPENDICES

#### 22.1 APPENDIX 1 – Schedule of Events Part I

Evaluation								
	Screening Days		Follow-up					
	-28 to -1	Day -112	Day 1	Day 2	Day 3	Day 4	Day 11/EOS  /ET	
Informed Consent	X						8791	
Inclusion/Exclusion Criteria	X	X						
Randomization		Х						
Demographics (Includes height, weight and BMI)	x							
Medical History	Х		0					
Physical Examination 	X	Х	0	X		X	Х	
Urine Drug Screen	X	X						
Alcohol test	Х	X 						
Serum Pregnancy Test	Х							
Urine Pregnancy Test		Х					Х	
Urinalysis	Х	Х		X				
FSH test (for post-menopausal women only)	х							
Clinical Laboratory Assessments (Chemistry and Hematology)	х	X		X		X	Х	
Serology (HIV, Hepatitis B and C)	Х							
Coagulation Panel (PT/INR)	Х							
Vital Signs 	Х	Х	$X^2$	X		Х	X	
12-Lead Electrocardiogram 	X 	Х	$X^4$	X		Х	X	
26 Hour Holter Monitoring 			Х					

Confidential

Indivior 10 December 2020

INDV-2000	
Clinical Study Protocol: INDV-2000-101	

Indivior 10 December 2020

Evaluation							
	Screening Days		Follow-up				
	-28 to -1	Day -1 	Day 1	Day 2	Day 3	Day 4	Day 11/EOS  /ET
PK Sampling 			X 	Х	X	Х	
Drug Administration 			Х				
AE Assessment		X	Х	X	X	X	Х
Concomitant Medication Assessment	X	X	Х	X	X	Х	Х
Admission to Clinical Unit		X					
Discharge from Clinical Unit						Х	

INDV-2000	
Clinical Study	Protocol: INDV-2000-101

Indivior 10 December 2020

Evaluation						1074134		ALC 1. 1	58 1552/1002			
		Period 1 - Dosing Under Fasting Condition				dition	Period 2 -	Dosing a	fter High-	and the second second second	ent Meal atient	Follow-up
	Screening Days -28 to -1	In clinical unit			Outpatient visits		In clinical unit			visits		
		Day -111	Day 1	Day 2	Day 3	Day 4	Day -1 	Day 1	Day 2	Day 3	Day 4	Day 10/EOS/ET 
Informed Consent	X											
Inclusion/Exclusion Criteria	X	x										
Demographics (Includes height, weight and BMI)	X											
Medical History	X											
Physical Examination 	Х	X		X			X		X			X
Urine Drug Screen	Х	X					X					
Alcohol test	X	X 					X 					
Urinalysis	Х	Х		Х			Х		Х			
Clinical Laboratory Assessments (Chemistry and Hematology)	x	x		x		x	x		x		x	х
Serology (HIV, Hepatitis B and C)	X											
Coagulation Panel (PT/INR)	х											
Vital Signs 	Х	X	X 	X		X	X	X	Х		Х	X

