## Subjects with ALT ≥3x ULN and bilirubin ≥2x ULN (>35% direct); or ALT ≥3x ULN and INR >1.5:

**This event is an SAE** and should be reported using the SAE Reporting Form (Section 11). Serum bilirubin fractionation should be performed, if testing is available. If fractionation is unavailable, urinary bilirubin is to be measured via dipstick (a measurement of direct bilirubin, which would suggest liver injury).

Make every reasonable attempt to have the subject return to the clinic within 24 hours for repeat liver chemistries, additional testing and close monitoring (with specialist or hepatology consultation recommended).

Monitor the subject twice weekly until liver chemistries (ALT, AST, alkaline phosphatase, bilirubin) resolve, stabilize or return to within baseline values.

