9.1.12 Clinical Laboratory Evaluations

Laboratory data will be presented using units as reported by the clinical laboratory.

Listings for each category of laboratory test [hematology, serum chemistry, urinalysis, serology, coagulation, urine drug screen and other laboratory tests (pregnancy and endocrinology)] will include test name, study visit, date and time of specimen collection, reference range, observed value, and alert flag. Separate listings will be done for abnormal on-study laboratory values and for CS on-study laboratory values.

Observed values and changes from baseline will be summarized by visit. Shifts from baseline will also be summarized.

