9.2 Analysis Timepoints

For Part I, the baseline value will be defined as the last non-missing evaluation prior to the first dose of IMP. For Part II, the period-specific baseline value will be the last non-missing evaluation prior to the first period-specific dose of IMP. If multiple measurements are collected at baseline with the same assessment time (or date if time is not available) then the mean of the measurements will be taken. All other analysis time points will be based on nominal visits.

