11 CHANGES TO PROTOCOL-SPECIFIED ANALYSES

Protocol:	SAP:
The number and percentage of subjects reporting TEAEs will be presented overall, by MedDRA system organ class (SOC) and preferred term (PT), each in descending order of frequency (then alphabetically in case of ties).	Sentence changed to: The number and percentage of subjects reporting TEAEs (incidence) and number of TEAEs will be presented both overall and by MedDRA SOC and PT, each in descending order of frequency (then alphabetically in case of ties).
IMP-related TEAEs, treatment-emergent SAEs (TESAEs), IMP-related TESAEs, TEAEs leading to death, TEAEs leading to IMP discontinuation, and TEAEs leading to IMP interruption will be presented both overall and by SOC and PT.	TEAEs leading to death, TEAEs leading to IMP discontinuation, and TEAEs leading to IMP interruption will be listed but not summarized.
TEAEs will also be summarized by intensity within SOC and PT.	Sentence changed to: TEAEs will also be summarized by maximum severity and by maximum toxicity grade within SOC and PT
In addition, TEAEs leading to death and IMP- related TEAEs leading to death will be summarized separately by PT	Removed.
	Added: Shifts from baseline in clinically abnormal results will also be summarized.
Concomitant therapies (medications) will be collected from screening until the EOS visit or the ET visit	Concomitant medications are defined as medications taken at or after the time of first IMP dose.
The PK analysis population is defined as subjects who received at least one dose of INDV-2000 and have an adequate number of PK samples collected to derive PK parameters.	Sentence changed to : The PK population is defined as subjects who received at least one dose of INDV-2000 and have an adequate number of PK samples collected to derive at least one PK parameter. Added:
	The Food Effect PK population will be defined as the subset of Part II subjects in the PK population that have at least one evaluable PK parameter for at least one meal condition.

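### Laboratory shift tables exclude unscheduled draws and have no worst-post-baseline category, so they may under-count abnormal results

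*SAP*

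**What the plan says.** The exclusion is the last sentence of the multiple-assessments bullet in SAP 9.1: "Assessments classified as 'unscheduled' will not be included in summary tables". The list containing that bullet is introduced by "The following general comments also apply to all statistical analyses and data presentations", so the rule reaches the laboratory tables.

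On laboratory shifts, SAP 9.1.12 says "Shifts from baseline will also be summarized", and SAP 11 records the addition as "Shifts from baseline in clinically abnormal results will also be summarized". Neither section defines a worst post-baseline value or exempts shifts from the exclusion. After defining baseline, SAP 9.2 adds: "All other analysis time points will be based on nominal visits".

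The protocol foresees laboratory draws outside the visit grid. For the combined ALT and bilirubin (or INR) criteria, Appendix 3 asks for a repeat within 24 hours and then says "Monitor the subject twice weekly until liver chemistries" have resolved, levelled off or come back to baseline. Its ALT-only category has a repeat at 24 to 72 hours and then weekly monitoring. Section 4.3 allows the Part I stay to be extended for safety reasons. None of these draws has a column in the schedules of events.

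**The concern.** Leaving unscheduled values out of by-visit means is sound, because it stops subjects with extra visits from distorting a time point. A shift table serves another purpose: it counts how many subjects moved from normal to abnormal, or to a worse category. Here the same exclusion removes values that were often obtained because something looked wrong.

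SAP Table 1 links the secondary objective on the maximum tolerated single dose to changes from baseline in laboratory, ECG, vital-sign and physical-examination data, and points to Sections 9.1.12 to 9.1.15 for the analysis. With six active subjects per cohort, one uncounted subject is visible in a comparison with pooled placebo.

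**Working it through.** The plan attaches no power, alpha or event-rate figure to this rule, so there is nothing to reproduce. The check compares the exclusion with the schedule and then sizes one subject.

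**Step 1. Which chemistry draws are scheduled after dosing?** From the schedules of events:
- Part I: Days 2, 4 and 11 (EOS/ET).
- Part II: Days 2 and 4 of each period, and Day 10 (EOS/ET).

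**Step 2. Do event-driven draws fall on those days?** As an illustration, assume a liver signal flagged on Day 4 of Part I and four weeks of follow-up.
- Twice weekly (every 3.5 days) from Day 5: Days 5, 8.5, 12, 15.5, 19, 22.5, 26, 29.5 and 33. That is 9 draws, 0 on a scheduled chemistry day and 7 after Day 11.
- Weekly from Day 7: Days 7, 14, 21, 28 and 35. That is 5 draws, 0 on a scheduled day and 4 after Day 11.

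These counts depend on the assumed start. A weekly series counted from Day 4 itself would reach Day 11. If the draws are classed as unscheduled, a peak after Day 4 can be tabulated only through the Day 11 value.

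**Step 3. When does the omission change a shift cell?** The SAP does not give the shift categories.
- If they follow the out-of-range flag in SAP 8.4 (normal, low, high, abnormal), the subject in Step 2 is already counted as high from Day 4. A higher unscheduled peak changes nothing.
- If they follow the toxicity grades in SAP Appendix 3, a scheduled ALT of 3 x ULN is Grade 2 (2.6 to 5.0) and an unscheduled 6 x ULN is Grade 3 (5.1 to 10). The cell for the worse category would miss this subject.
- Under either scheme, a subject whose scheduled values are all in range and whose only out-of-range value is unscheduled is missed.

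**Step 4. How much is one missed subject?** The weight is 1/n. The limits are exact (Clopper-Pearson) 95% limits; for 0/n the upper limit is 1 − 0.025^(1/n).

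| Group | n | Tabulated as planned | If the value counted | Change |
|---|---|---|---|---|
| Part I active cohort | 6 | 0/6 = 0% (0 to 45.9%) | 1/6 = 16.7% (0.4 to 64.1%) | 16.7 points |
| Part II, one condition | 8 | 0/8 = 0% (0 to 36.9%) | 1/8 = 12.5% (0.3 to 52.7%) | 12.5 points |
| Pooled placebo, up to 9 × 2 | 18 | 0/18 = 0% (0 to 18.5%) | 1/18 = 5.6% (0.1 to 27.3%) | 5.6 points |

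**Step 5. Is the value recovered elsewhere?** SAP 9.1.12 lists abnormal and clinically significant on-study values. SAP 9.1.9 tabulates TEAEs by maximum severity and maximum toxicity grade. No SAP section returns an unscheduled value to a laboratory summary or shift table. A repeat filed under a nominal visit follows the closest-in-time rule, or the mean if equidistant, and neither selects the worst value.

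**The case against.** The strongest reply is that serious laboratory signals reach the tables by another route. Protocol 10.1.4 makes a laboratory change reportable as an AE when, among other conditions, it needs further diagnostic testing, which Appendix 3 requires for subjects meeting its stopping criteria. The combined ALT and bilirubin or INR picture is an SAE outright. Laboratory AEs are graded, and Part I TEAEs have no end date, so a peak found at an unscheduled draw can appear under the primary endpoint. This stands. A reader might infer that signal-driven values appear in no table at all, and the documents do not support that. What remains is that the AE route depends on the abnormality being reported as an AE and counts preferred terms, not shifts from baseline. The listings keep every abnormal value but do not compare cohorts with placebo.

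A second reply is that scheduled-only shifts are coherent beside by-visit summaries, and that the SAP does not define what counts as unscheduled. Both points are fair. The table shells are in a separate document and the schedule footnotes are not in the available text, so the classification of repeats is an assumption.

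A reader might also infer that the rule biases all safety summaries toward normal. That is not shown. Dropping a confirmatory repeat that turns out normal keeps the abnormal scheduled value, so by-visit means could move either way. Only a count of worst categories is affected in one direction.

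Nor does the point extend with the same force to ECGs and vital signs. Protocol 8.6 does say "Additional measurements may be taken as deemed necessary by the Investigator", and Section 8.5 allows the same for vital signs. But the SAP plans shifts only for laboratory data, and an ECG triplicate triggered at a scheduled time point is averaged and summarised under SAP 9.1.15.

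**Conclusion.** The concern holds as possible under-counting in the laboratory shift tables, not as loss of data. The rule is explicit, applies generally and has no exception for shifts, and no worst-post-baseline category exists.

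The 16.7-point change in an active cohort (12.5 points in Part II) is the effect of one subject and needs two conditions: the draw is classed as unscheduled, and it is that subject's only out-of-range or worse-category value. A peak on a scheduled day, or a higher unscheduled value in a category already reached, changes nothing. How often both conditions would be met cannot be estimated from the documents. Because the tables serve a stated objective and the remedy is cheap, the change is worth making.

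**What to change.** Keep the by-visit summaries scheduled-only. Add to SAP 9.1.12: *A shift from baseline to the worst post-baseline value will be summarised using scheduled and unscheduled assessments from dosing to EOS/ET or last follow-up (Part II: by period, using the TEAE windows in Section 9.1.9).* Add a matching exception to the last sentence of the multiple-assessments bullet in SAP 9.1, and state the shift categories.

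One detail needs settling for Part II. The Period 2 TEAE window lasts as long as the interval between the two doses. With the minimum one-week interval it closes 7 days after dosing, whereas Day 10 is 10 − 1 = 9 days after dosing. The sentence should say whether the EOS value and later follow-up count toward Period 2.

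The cost is one sentence, one exception and one extra shift row per parameter. The downside is that subjects measured more often have more chances of an extreme value; a footnote should say so. Maximum post-dose QTcF and vital-sign summaries would be optional new analyses, not part of this correction. The change belongs in the SAP before database lock and unblinding, because SAP 9 treats analyses performed after either and not described in the plan as post hoc and exploratory.
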